**11.3.5. Safety**

- For a given subject and the analysis of solicited symptoms during the 7 day follow-up period after vaccination, missing or non-evaluable measurements will not be replaced. Therefore, the analysis of the solicited symptoms based on the ES will include only vaccinated subjects with documented safety data (*i.e.*, symptom screen completed). More specifically the following rules will be used:
  - Subjects who documented the absence of a solicited symptom after one dose will be considered not having that symptom after that dose.
    - Subjects who documented the presence of a solicited symptom and fully or partially recorded daily measurement over the solicited period will be included in the summaries at that dose and classified according to their maximum observed daily recording over the solicited period.
    - Subjects who documented the presence of a solicited symptom after one dose without having recorded any daily measurement will be considered as having symptom and will be considered in subjects who experiences the symptom but will not be considered in the specific information by grade.
    - Doses without symptom sheets documented will be excluded.
- For analysis of unsolicited AEs, SAEs and for the analysis of concomitant medications, all vaccinated subjects will be considered. Subjects who did not report an event or concomitant medication will be considered as subjects without the event or the concomitant medication respectively.
- Related dose: The related dose for an event (e.g., AE, medication, vaccination...) is the study dose given before an event. In case the event takes place on a day a study dose is given, the related dose will be that of the study dose even if the event actually took place before. For instance, for a conc. medication started on the day of study dose 2 but before dose 2 administrations, the related dose will be dose 2.
- The maximum intensity of local injection site redness and swelling will be scored at GSK Biologicals as follows:
  - 0 : None
  - 1 : < 5 mm
  - 2 : 5 to 20 mm
  - 3 : > 20 mm
- Fever is defined as temperature  $\geq 37.5^{\circ}\text{C}$  /  $99.5^{\circ}\text{F}$  for oral, axillary or tympanic route, or  $\geq 38.0^{\circ}\text{C}$  /  $100.4^{\circ}\text{F}$  for rectal route. The preferred route for recording temperature in this study will be axillary. For the analysis, temperatures will be coded as follows:

Grade	Temperature (oral, axillary or tympanic route)	Temperature (rectal route)
0	< 37.5°C	< 38°C
1	$\geq 37.5^{\circ}\text{C}$ - $\leq 38.5^{\circ}\text{C}$	$\geq 38^{\circ}\text{C}$ - $\leq 39^{\circ}\text{C}$
2	$> 38.5^{\circ}\text{C}$ - $\leq 39.5^{\circ}\text{C}$	$> 39^{\circ}\text{C}$ - $\leq 40^{\circ}\text{C}$
3	$> 39.5^{\circ}\text{C}$	$> 40^{\circ}\text{C}$

- **Conversion of temperature to °C**
  - Temperature in °Celsius = ((Temperature in °Fahrenheit -32) \*5)/9.
  - The result is rounded to 1 decimal.
- Note that for all tables described in this section, the way the percentage of subjects will be derived will depend on the event analysed (see table below for details). As a result, the N value will differ from one table to another.

Event	N used for deriving % per subject for Vaccination phase	N used for deriving % per dose for Vaccination phase
Concomitant vaccination	All subjects with study vaccine administered	All study visits with study vaccine administered
Solicited general symptom	All subjects with at least one solicited general symptom documented as either present or absent (i.e., symptom screen completed)	All study visits with study vaccine administered and with at least one solicited general symptom documented as either present or absent (i.e., symptom screen completed)
Solicited local symptom	All subjects with at least one solicited local symptom documented as either present or absent (i.e., symptom screen completed)	All study visits with study vaccine administered and with at least one solicited local symptom documented as either present or absent (i.e., symptom screen completed)
Unsolicited symptom	All subjects with study vaccine administered	All study visits with study vaccine administered
Concomitant medication	All subjects with study vaccine administered	All study visits with study vaccine administered

- All CI computed will be two-sided 95% CI.
- Grading of haematological and biochemical parameters will be assessed as per the following tables: -

**Table 4 Toxicity grading scales for hematology and biochemistry parameters applicable for this study**

Component	Grade 1	Grade 2	Grade 3	Grade 4
Hemoglobin (g/dL)	9.0 to < 10.5	8.0 to < 9.0	7.0 to < 8.0	< 7.0
Leukocytes decreased (cell/mm  )	2500 to < 3500	1500 to < 2500	1000 to < 1500	< 1000
Platelets decreased (cell/mm  )	75000 to < 150000	50000 to < 75000	25000 to < 50000	< 25000
Alanine Aminotransferase (increase by factor)	1.1 to < 2.0 xULN	2.0 to < 3.0 xULN	3.00 to ≤ 8.0 xULN	> 8.0 xULN
Aspartate Aminotransferase (increase by factor)	1.1 to < 2.0 xULN	2.0 to < 3.0 xULN	3.00 to ≤ 8.0 xULN	> 8.0 xULN
Creatinine (mg/dL)	0.6 to < 0.9	0.9 to < 1.2	1.2 to ≤ 1.5	> 1.5
Absolute neutrophil count decreased (cell/mm^3)	1000 to < 1300	750 to < 1000	500 to < 750	< 500
Absolute lymphocyte count decreased (cell/mm^3)	600 to < 650	500 to < 600	350 to < 500	< 350
Eosinophil	N.A	N.A	N.A	N.A
Basophil	N.A	N.A	N.A	N.A
Monocyte	N.A	N.A	N.A	N.A

Grading scale adapted from [Error! Reference source not found., 2003], [Error! Reference source not found., 2004] and [Error! Reference source not found., 2007].

ULN: upper limit of normal

**11.3.6. RTI and LRTI**

- For the analysis of RTI and LRTI, all cases will be definitively classified as either RSV-RTI, RSV-LRTI, RSV-severe LRTI or RSV-very severe LRTI according to standardized case definitions (see table below) based on the available WHO case definitions, and the association to RSV infection will be assessed by quantitative PCR as primary analysis.

**Table 5 Case definition of RSV- RTI/LRTI**

RSV infection	Symptomatic and/or asymptomatic RSV infection
RSV-RTI	Runny nose OR blocked nose OR cough AND Confirmed RSV infection 
RSV-LRTI	History of cough OR difficulty breathing  AND SpO 2 < 95%  , OR RR increase  AND Confirmed RSV infection 
RSV-severe LRTI	Meeting the case definition of RSV-LRTI AND SpO 2 < 93%  , OR lower chest wall in-drawing
RSV-very severe LRTI	Meeting the case definition of RSV-LRTI AND SpO 2 < 90%  , OR inability to feed, OR failure to respond / unconscious
RSV hospitalization	Confirmed RSV infection  AND Hospitalized for acute medical condition 
All-cause LRTI	History of cough OR difficulty breathing  AND SpO 2 < 95%  , OR RR increase 

Definition based on [Modjarrad, 2016]

LRTI = lower respiratory tract infections; RR = respiratory rate; RTI = respiratory tract infections;

SpO2 = blood oxygen saturatin

 Based on history reported by parents/LARs and includes difficulty breathing (e.g. showing signs of wheezing or stridor, tachypnoea, flaring [of nostrils], chest in-drawing, apnoea) associated with nasal obstruction

 For blood oxygen saturation (SpO2), the lowest value monitored will be used

 RR increase defined as ≥ 40/minute (12 months of age or above)

 RSV infection confirmed on nasal swab positive for RSV A or B by quantitative Reverse Transcription Polymerase Chain Reaction (qRT-PCR)

 RSV sampling and testing is based on medical judgment of medical practitioner or driven by algorithm

 Hospitalization is defined as a medical decision that the infant requires admission for observation or treatment

- For the analysis of RSV-RTI episode, the start date of an RTI episode will be defined as the first day of any occurrence of cough, runny nose, blocked nose, and a new case requires an interval of at least 7 symptom free days since the last episode of RTI that was diagnosed.
- For the analysis of RSV-LRTI or severe or very severe LRTI the start date of the LRTI episode is defined as the point at which the first symptoms of cough, or difficulty breathing were observed and a new case requires an interval of at least 7 symptom free days since the last episode of LRTI that was diagnosed.

- End date of the RTI episode is defined as the point at which the child is considered symptom-free of cough, runny nose, blocked nose, wheezing, and difficulty breathing.
- For molecular biology (qRT-PCR test), the following cut-off will be applied: -

System	Component	Method	Unit	Cut-off
Nasal swab	RSV-A RNA	Quantitative real-time PCR (qRT-PCR)	Copies/ml	1123
Nasal swab	RSV-B RNA	Quantitative real-time PCR (qRT-PCR)	Copies/ml	1467

- For calculation of viral load for RSV-A/B, all reported values will be included. Subject infected by either RSV-A or RSV-B or both will be included for calculation. Total viral load = Viral load for RSV-A + Viral load for RSV-B. LOD for RSV-A and RSV-B are 1123 and 1467 copies/ml, respectively. Following rule will be applied: -

Raw result	Derivation for positivity	Derivation for viral load calculation
<LOD	NEG	LOD/2
≥LOD	POS	Exact value

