First, F protein antigens purified from CHO expression system are coated onto 96-well microplates. Then, after a washing and a blocking step, serial two-fold dilutions of test sera, positive control serum, and palivizumab antibody reference standard are added in sequence with competitor antibodies (horseradish peroxidase-conjugated palivizumab) and incubated to allow specific binding of antibodies directed against the F protein antigens. If palivizumab-like antibodies are present in serum samples, they will compete with the horseradish peroxidase-conjugated palivizumab antibodies for binding to the F protein coated antigen. After a washing step, the horseradish peroxidase substrate solution (TMB/H₂O₂) is added and a colored product develops in a manner that is inversely proportional to the amount of palivizumab-like antibodies contained in the test serum. The color is quantified by reading the optical densities at 450-620 nm using a spectrophotometer. Antibody concentrations of individual serum and control samples are determined after interpolation from the ELISA standard curve using a four-parameter equation and are expressed as palivizumab-equivalent antibodies in microgram per millilitre (µg/mL).

PCR

- Quantitative PCR able to discriminate RSV-A and RSV-B subtypes:

Briefly, RSV A and RSV B RNAs extracted from the nasal swabs are detected in a duplex PCR format using specific amplification primers and fluorescent probes designed in the RSV N gene, encoding the RSV nucleocapsid protein. The process involves nucleic acids extraction, conversion of RNA to complementary deoxyribonucleic acid by reverse transcription and detection by real-time PCR reaction using a calibration curve (absolute quantitation). The RSV viral load is reported as copies of RSV RNA per mL of sample.

- Qualitative multiplex PCR for detection of a panel of viruses.

A qualitative PCR multiplex assay is used for the detection and identification of multiple respiratory virus nucleic acids in nasal swabs from individuals suspected of respiratory tract infections. The following virus types and subtypes can be identified in the assay:

- Influenza A virus (Flu A)
- Influenza B virus (Flu B)
- Human Influenza A virus subtype H1 (Flu A-H1)
- Human Influenza A virus subtype H3 (Flu A-H3)
- Human Influenza A virus subtype H1pdm09 (Flu A-H1pdm09)
- Human respiratory syncytial virus A (RSV A)
- Human respiratory syncytial virus B (RSV B)
- Human adenovirus (AdV)
- Human metapneumovirus (MPV)

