**Template 47 Descriptive statistics of viral load calculated on all qRT-PCR confirmed RSV infection episodes with varying disease severity from vaccination dose 1 up to D366/D731 <Exposed Set>**

Symptoms	Parameters	Group N=		
		Value	LL	UL
RSV asymptomatic* (Excluding RSV-RTI, RSV-LRTI, RSV-severe LRTI or RSV-very severe LRTI)	n			
	GM			
	95% CI			
	SD			
	Q1			
	Median			
	Q3			
	Min/Max			
RSV RTI (Excluding RSV-LRTI, RSV-severe LRTI or RSV-very severe LRTI)				
RSV LRTI (Excluding RSV-severe or RSV-very severe LRTI)				
RSV-severe LRTI (Excluding RSV-very severe LRTI)				
RSV-very severe LRTI				
RSV hospitalization§				

RSV-Ld = Low dose ChAd155-RSV vaccine (5 x 10^9 vp)  
 RSV-Md = Middle dose ChAd155-RSV vaccine (1.5 x 10^10 vp)  
 RSV-Hd = High dose ChAd155-RSV vaccine (5 x 10^10 vp)  
 Placebo-Ld = Non-active control (0.5 ml)  
 Placebo-Md = Non-active control (0.15 ml)  
 Placebo-Hd = Non-active control (0.5 ml)  
 RSV = ChAd155-RSV vaccine (low/ middle/high dose pooled groups)  
 Placebo = Non-active control (0.5/0.15/0.5 ml pooled groups)  
 N = number of RSV infections episodes in each group  
 n= Number of events in each category  
 SD=Standard Deviation  
 Q1 and Q3 = 1st and 3rd quantiles  
 Min/Max = Minimum/Maximum  
 GM = Geometric mean

LL, UL for GM = Exact 95% Lower and Upper confidence limits  
 Total RSV viral load computed as RSV A Viral load + RSV B Viral load

\* Association to RSV based on central testing only for asymptomatic visit (no local test available)

§Confirmed RSV infection and hospitalized for acute medical condition

Please note: each episode for a subject is considered to be independent. We may have multiple swab for one episode. We have considered the swab with maximum viral load from one episode for the table

Please note – Except for RSV hospitalization, single episode is considered in single category of highest severity based on the symptom experienced

Please check:- To check for cases where asymptomatic swab has been taken but the subject hasve symptoms of RTI or LRTI. In this case, asymptomatic is also considered as RSV RTI/LRTI and maximum viral load of all the episode should be considered.

**Template 48 Descriptive statistics of maximum viral load per subjects based on qRT-PCR confirmed episode with varying disease severity form vaccination dose 1 up to D366/D731 <Exposed Set>**

	Parameters	Each Group		
		N=	95% CI	
Symptoms	Value	LL	UL	

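### Total RSV viral load adds half the detection limit of the negative subtype, so every single-subtype infection is overstated, by up to 65% for RSV-A alone at its detection limit.

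*SAP*

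**What the plan says.** SAP section 11.3.6 (RTI and LRTI) gives the viral-load derivation in four parts.

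- Who is included: "Subject infected by either RSV-A or RSV-B or both will be included for calculation".
- How the subtypes are combined: "Total viral load = Viral load for RSV-A + Viral load for RSV-B".
- The limits: "LOD for RSV-A and RSV-B are 1123 and 1467 copies/ml, respectively".
- A small derivation table. A result below the LOD is negative for positivity but takes the value LOD/2 for viral load. A result at or above it is handled as "≥LOD POS Exact value".

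The footnotes to Templates 47 and 48 (SAP section 13.2) repeat the sum: "Total RSV viral load computed as RSV A Viral load + RSV B Viral load". Neither section 11.3.6 nor the footnotes make an exception for the negative subtype when only one subtype is present.

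Protocol Appendix A describes the assay: "RSV A and RSV B RNAs extracted from the nasal swabs are detected in a duplex PCR format". A swab from an infant with one subtype therefore also has a result for the other, normally below its LOD.

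**The concern.** Half-LOD substitution is a reasonable stand-in for a single analyte that may be present but too low to detect. Here it is a term added to a different analyte that has already been measured. The total for an RSV-A-only infection contains RSV-B that the SAP's own table calls negative, and the reverse holds for RSV-B.

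The amount added is fixed, so it matters most where loads are low. Templates 47 and 48 report geometric mean, quartiles, median, minimum and maximum by severity category, from asymptomatic to very severe. An upward shift confined to low loads raises the lower end of these summaries and narrows the differences between categories if the milder ones carry lower loads. The shift also differs by subtype, so two groups or seasons with different subtype mixes would not be treated identically. A reported minimum could not be matched to the swab it came from.

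**Working it through.** The plan states no figure of its own for this effect, so there is nothing to reproduce. All inputs come from SAP section 11.3.6.

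**Inputs**
- LOD: RSV-A 1,123 copies/ml; RSV-B 1,467 copies/ml.
- Value given to a negative subtype: LOD/2, that is 1,123/2 = 561.5 for RSV-A and 1,467/2 = 733.5 for RSV-B.

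**Formulas**, for a single-subtype infection with measured load *v* and added amount *a* (733.5 for RSV-A only, 561.5 for RSV-B only):
- reported total = *v* + *a*
- overstatement = *a*/*v*
- shift on the log scale = log10((*v* + *a*)/*v*)

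**Results**

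| Infection | Measured load (copies/ml) | Reported total | Overstatement | log10 shift |
|---|---|---|---|---|
| RSV-A only | 1,123 (LOD) | 1,856.5 | 65.3% | 0.218 |
| RSV-A only | 2,246 | 2,979.5 | 32.7% | 0.123 |
| RSV-A only | 10,000 | 10,733.5 | 7.3% | 0.031 |
| RSV-A only | 100,000 | 100,733.5 | 0.73% | 0.003 |
| RSV-B only | 1,467 (LOD) | 2,028.5 | 38.3% | 0.141 |
| RSV-B only | 2,934 | 3,495.5 | 19.1% | 0.076 |
| RSV-B only | 10,000 | 10,561.5 | 5.6% | 0.024 |
| RSV-B only | 100,000 | 100,561.5 | 0.56% | 0.002 |

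The overstatement drops below 1% above 733.5/0.01 = 73,350 copies/ml for RSV-A only and above 561.5/0.01 = 56,150 for RSV-B only.

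**Floor.** The smallest total that can be reported is 1,856.5 for an RSV-A-only infection and 2,028.5 for an RSV-B-only infection, against LODs of 1,123 and 1,467.

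**Compression of ratios.** Two RSV-A-only loads of 1,123 and 11,230 differ tenfold. They are reported as 1,856.5 and 11,230 + 733.5 = 11,963.5, a ratio of 11,963.5/1,856.5 = 6.4.

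**Dependence on subtype.** A measured 2,000 copies/ml is reported as 2,733.5 if it is RSV-A and 2,561.5 if it is RSV-B, a difference of 172.

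**With the negative subtype counted as 0**, the total equals the measured load in every row and the overstatement is 0. Infections positive for both subtypes are the same under either rule.

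**The case against.** The case for leaving this alone is mostly about importance, and much of it stands.

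- Viral load is not an endpoint. SAP section 7 calls all analyses descriptive, and positivity is derived separately, so no infection is gained or lost and no decision rule moves. This stands.
- The 65% applies only to RSV-A alone, exactly at its LOD. This stands, and the table above shows how quickly the excess fades.
- Template 47 takes the swab with the highest load in an episode and Template 48 the highest per subject, which moves values away from the LOD. This stands where there are several swabs, but does not help single-swab episodes.
- Protocol section 11.10 and SAP section 6.3 ask for mean, median, minimum and maximum; geometric means and quartiles appear only in the templates. On the arithmetic scale the rule adds at most 733.5 copies/ml. This is correct, but the minimum is affected either way and the templates define what will be produced.
- The rule applies equally to vaccine and placebo, which are randomised 1:1 within each step. No systematic advantage to either arm has been shown.
- Templates 34 and 51 list the central RSV-A and RSV-B results in separate columns, so the raw results are not lost. The floor applies only to the derived total.
- Half-limit substitution is the SAP's convention elsewhere, and a result below the LOD is not proof of zero. That is fair for one censored assay. Inside a sum that already has a measured positive component, 0 fits the SAP's own negative classification better than 561.5 or 733.5.

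One could also say that a programmer would not add the negative subtype. Nothing in the SAP says so, and two programmers could produce different tables.

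**Conclusion.** The concern holds. Followed as written, SAP section 11.3.6 overstates the total load of every single-subtype infection by a fixed 733.5 (RSV-A only) or 561.5 (RSV-B only) copies/ml. That is at most 65% and 38% respectively, and negligible at 100,000 copies/ml and above. It is a minor point, confined to descriptive tables.

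The conclusion rests on two readings: that the LOD/2 rule applies to both terms of the sum, since no exception is written, and that both subtypes are reported for each swab, as the duplex assay implies. How far group medians, quartiles or geometric means would move cannot be determined, because neither document gives an expected load distribution. That asymptomatic or mild infections have the lower loads, and so would be most affected, is an assumption.

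**What to change.** In SAP section 11.3.6, define total viral load as the sum over those subtypes at or above their own LOD, so that a subtype below its LOD contributes 0 when the other is positive. Put the same wording in the footnotes to Templates 47 and 48. A swab with both subtypes below their LODs is not a qRT-PCR-confirmed infection and does not enter these tables, so no substitute value is needed there.

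The cost is one line of text, two footnotes and the matching line in the derivation program. No new data are needed.

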**11.3.7. Number of decimals displayed**

The following decimal description from the decision rules will be used for the demography, immunogenicity and safety/reactogenicity.

Display Table	Parameters	Number of decimal digits
Demographic characteristics	Mean, median age	1
Demographic characteristics	SD (age)	1
Reactogenicity	Mean, Min, Q1, Median, Q3, Max for duration	1
All summaries	% of count, including LL & UL of CI	1
All summaries	% of difference, including LL & UL of CI	2

## 12. ANNEX 2: RELEVANT PREFERRED TERMS FOR DETECTION OF AESI

Any of the below listed preferred term reported as an Expedited Adverse Event must be immediately escalated to the CRDL or Central Safety Physician to assess or confirm the need for an urgent IDMC review.

The list of preferred terms and associated PT codes is given below:

**HAEMORRHAGE**

Preferred term	PT code
abdominal wall haemorrhage	10067788
acute haemorrhagic conjunctivitis	10067817
administration site haemorrhage	10075101
adrenal haemorrhage	10001361
anal haemorrhage	10049555
anastomotic haemorrhage	10056346
angina bullosa haemorrhagica	10064223
application site haemorrhage	10072694
arterial haemorrhage	10060964
basal ganglia haemorrhage	10067057
bone marrow haemorrhage	10073581
brain stem haemorrhage	10006145
brain stem microhaemorrhage	10071205
breast haemorrhage	10006254
bronchial haemorrhage	10065739
catheter site haemorrhage	10051099
central nervous system haemorrhage	10072043
cerebellar haemorrhage	10008030
cerebellar microhaemorrhage	10071206
cerebral haemorrhage	10008111
cerebral microhaemorrhage	10067277
cervix haemorrhage uterine	10050022
ciliary body haemorrhage	10057417
conjunctival haemorrhage	10010719
diverticulitis intestinal haemorrhagic	10013541
diverticulum intestinal haemorrhagic	10013560
duodenitis haemorrhagic	10013865
ear haemorrhage	10014009
encephalitis haemorrhagic	10014589
gastric haemorrhage	10017788
gastroduodenal haemorrhage	10053768
gastrointestinal haemorrhage	10017955
genital haemorrhage	10061178
haemarthrosis	10018829
haematemesis	10018830
haematochezia	10018836
haematotympanum	10063013
haematuria	10018867
haemorrhage	10055798
haemorrhage coronary artery	10055803

haemorrhage intracranial	10018985
haemorrhage subcutaneous	10018999
haemorrhage subepidermal	10019001
haemorrhage urinary tract	10055847
haemorrhagic anaemia	10052293
haemorrhagic diathesis	10062713
haemorrhagic disorder	10019009
haemorrhagic infarction	10019013
haemorrhagic ovarian cyst	10060781
haemorrhagic pneumonia	10077933
haemorrhagic thyroid cyst	10072256
haemorrhagic urticaria	10059499
injection site haemorrhage	10022067
internal haemorrhage	10075192
intestinal haemorrhage	10059175
intra-abdominal haemorrhage	10061249
intraventricular haemorrhage	10022840
iris haemorrhage	10057418
joint microhaemorrhage	10077666
lacrimal haemorrhage	10069930
large intestinal haemorrhage	10052534
laryngeal haemorrhage	10065740
lip haemorrhage	10049297
lower gastrointestinal haemorrhage	10050953
lymph node haemorrhage	10074270
mediastinal haemorrhage	10056343
mesenteric haemorrhage	10060717
mouth haemorrhage	10028024
mucocutaneous haemorrhage	10076048
mucosal haemorrhage	10061298
muscle haemorrhage	10028309
myocardial haemorrhage	10048849
naevus haemorrhage	10062955
ocular retrobulbar haemorrhage	10057571
oesophageal haemorrhage	10030172
optic disc haemorrhage	10030919
optic nerve sheath haemorrhage	10030941
ovarian haemorrhage	10065741
pancreatic haemorrhage	10033625
papillary muscle haemorrhage	10059164
parathyroid haemorrhage	10059051
parotid gland haemorrhage	10051166

pelvic haemorrhage	10063678
penile haemorrhage	10034305
pericardial haemorrhage	10034476
periorbital haemorrhage	10071697
peritoneal haemorrhage	10034666
petechiae	10034754
pharyngeal haemorrhage	10034827
pituitary haemorrhage	10049760
post procedural haemorrhage	10051077
procedural haemorrhage	10071229
prostatic haemorrhage	10036960
pulmonary alveolar haemorrhage	10037313
pulmonary haemorrhage	10037394
putamen haemorrhage	10058940
rectal haemorrhage	10038063
renal haemorrhage	10038460
respiratory tract haemorrhage	10038727
retinal haemorrhage	10038867
retroperitoneal haemorrhage	10038980
scleral haemorrhage	10050508
skin haemorrhage	10064265
small intestinal haemorrhage	10052535
soft tissue haemorrhage	10051297
spermatic cord haemorrhage	10065742
spinal cord haemorrhage	10048992
spinal epidural haemorrhage	10049236
spinal subarachnoid haemorrhage	10073564
spinal subdural haemorrhage	10073563
splenic haemorrhage	10041647
spontaneous haemorrhage	10074557
subarachnoid haemorrhage	10042316
subdural haemorrhage	10042364
testicular haemorrhage	10051877
thalamus haemorrhage	10058939
thoracic haemorrhage	10062744
thyroid haemorrhage	10064224
tongue haemorrhage	10049870
tracheal haemorrhage	10062543
upper gastrointestinal haemorrhage	10046274
ureteric haemorrhage	10065743
urethral haemorrhage	10049710
urinary bladder haemorrhage	10046528

urogenital haemorrhage	10050058
uterine haemorrhage	10046788
vaccination site haemorrhage	10069475
vaginal haemorrhage	10046910
venous haemorrhage	10065441
vitreous haemorrhage	10047655
vulval haemorrhage	10063816

